**Post-market Clinical Follow-up Study to
Provide Safety, Performance and Clinical
Benefits Data of the DVR® Plating System
(Implant and Instrumentation)**

A Retrospective Consecutive Series Study

Revision 1

08/05/2019

NCT04653051

STUDY SPONSOR

**Zimmer GmbH
[name]
P.O. Box
[name]
Switzerland
[contact]**

Clinical Investigation Plan

Title:	Post-market Clinical Follow-up Study to Provide Safety, Performance and Clinical Benefits Data of the DVR® Plating System (Implant and Instrumentation) – A Retrospective Consecutive Series Study
CIP ID:	MDRG2017-89MS-14T
Sponsor:	Zimmer GmbH
Manufacturer:	Biomet Trauma, Warsaw, Indiana, USA
Objectives:	
The objective of this retrospective PMCF study is to collect data confirming safety, performance and clinical benefits of the DVR Plating System (implant and instrumentation) when used for the treatment of wrist fractures.
 
The primary objective is the assessment of performance by analyzing fracture healing.
 
The secondary objectives are the assessment of safety by recording and analyzing the incidence and frequency of complications and adverse events. Relation of the events to implant, instrumentation and/or procedure should be specified. Patients' outcomes will also be assessed.

Population:	Consecutive series of subjects implanted with one of the DVR Plating System according to the approved/cleared indications. Inclusion/exclusion criteria are in accordance to the indications and contraindications in the IFU. The devices included in the study will be the ones used in accordance with their IFU and/or Zimmer Biomet's approved labeling.
Inclusion/Exclusion Criteria	
Inclusion Criteria:
 
All subjects must have been implanted with one of the DVR Plates according to the approved indications.

Clinical Investigation Plan

	
Exclusion Criteria:
 
- Off-label use- Cases where there is an active infection- Conditions which tend to retard healing such as, blood supply limitations, previous infections, etc- Insufficient quantity or quality of bone to permit stabilization of the fracture- Conditions that restrict the patient's ability or willingness to follow postoperative instructions during the healing process- Foreign body sensitivity – where material sensitivity is suspected, appropriate tests should be conducted and sensitivity ruled out prior to implantations- Cases where the implant(s) would cross open epiphyseal plates in skeletally immature patients- Cases with malignant primary or metastatic tumors which preclude adequate bone support or screw fixations, unless supplemental fixation or stabilization methods are utilized 
Study Design: Single-center, Retrospective, Consecutive series
 
Clinical Phase: Post-market
 
Number of Subjects: 115 cases (in 111 patients) implanted with the DVR Plating System:
 
Length of Study: 12 months overall:
- Ethics Committee approval, patients' identification, consent and enrollment into the study- Collection of baseline information available in medical notes from the pre-OP condition to the immediate post-OP and last consultation visit- Conduct follow-up phone calls, data collection, analysis, and final report

--	--

Clinical Investigation Plan

Study Device: DVR Plates:

DVR Crosslock Plates (and respective instrumentation)

Narrow Mini Locked Plate

Extra Narrow Locked Plate

Mini Locked Plate

Narrow Locked Plate

Standard Locked Plate

Wide Locked Plate

Medium Locked Plate

Long Locked Plate

Extra Long Locked Plate

Extra Extra Long Locked Plate

Clinical Investigation Plan

DVR Wrist Plates (and respective instrumentation)

Dorsal Plate

Radial Styloid Plate

Ulna Plate

DVR Volar Rim Plates (and respective instrumentation)

DVR Volar Rim

DVR Volar Rim Narrow

Score: Patient-Rated Wrist Evaluation Score (PRWE)

Documentation: Paper / electronic

Statistical Analysis: Data collected in the study will be summarized descriptively. Continuous data (e.g. age) will be summarized through means, medians, standard deviation, minimum, maximum and 95% confidence intervals (CIs).

Clinical Investigation Plan

Categorical data (e.g. gender) will be summarized using counts, percentages and 95% confidence limits. Summaries of fracture healing and osteotomy rates, implant related revision rates and complication data will be presented as frequencies and percentages.

References

1. Clinical Investigation of medical devices for human subjects – Good Clinical practice. ISO 14155:2011.

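### Could the undated exclusion criteria and the unlabelled count of 115 cases distort the reported healing rate?

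*Combined protocol and SAP*

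**What the plan says.** All the relevant text is in the synopsis of the Clinical Investigation Plan.

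- **Objectives.** "The primary objective is the assessment of performance by analyzing fracture healing". Safety is secondary and is assessed by "recording and analyzing the incidence and frequency of complications and adverse events".
- **Population.** "Inclusion/exclusion criteria are in accordance to the indications and contraindications in the IFU". The inclusion criterion requires that the plate was implanted within its approved indications.
- **Exclusion Criteria.** Three items carry no assessment date: "Cases where there is an active infection", "Conditions which tend to retard healing such as, blood supply limitations, previous infections, etc" and "Conditions that restrict the patient's ability or willingness to follow postoperative instructions during the healing process". A fourth, "Insufficient quantity or quality of bone to permit stabilization of the fracture", is also undated but is worded from the decision to fix the fracture. The foreign-body item is the only one with explicit timing: sensitivity is to be ruled out before the implant is placed. The list opens with off-label use.
- **Number of Subjects.** "115 cases (in 111 patients) implanted with the DVR Plating System". No stage (identified, eligible or consented) is attached to the figure.
- **Length of Study.** Patient identification, consent and enrollment come first in the list. Collection from the medical notes comes next, then the follow-up calls.
- **Statistical Analysis.** Everything is descriptive. Categorical data get counts, percentages and 95% confidence limits, and healing is reported as a frequency and a percentage.

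**The concern.** In a prospective study eligibility is normally settled before any outcome exists, so an undated criterion does little harm. Here the surgery is in the past and the notes run to the last consultation. The person judging eligibility may therefore be able to see whether the fracture healed, whether an infection followed and whether the patient complied. Three of the undated exclusions concern infection, impaired healing and compliance, which overlap with the outcomes or plausibly influence them. The open ending of the healing item seems to leave room for discretion.

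If a post-operative infection or a delayed union could be read as an exclusion, non-healed cases would leave the denominator and the healing percentage would rise by construction. An unlabelled count of 115 would make this harder to see, because a reader could not tell whether cases had already been removed. The healing percentage is the main result, so its denominator deserves scrutiny.

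**Working it through.** **Step 1. When are the exclusions judged?** The passages, set side by side, point one way.

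1. The Population entry ties the criteria to the indications and contraindications of the device. A contraindication to an implant is weighed when deciding whether to implant.
2. Off-label use describes how the device was used at surgery. The bone-quality, open-growth-plate and tumor items concern whether fixation is suitable in the first place. The sensitivity item is explicitly pre-implantation.
3. Within the three contested items, previous infections look backward. The compliance item excludes *conditions* that limit the patient, not observed non-compliance.
4. The Objectives make complications and adverse events an outcome to be counted. Treating a post-operative infection as an exclusion would defeat that objective.
5. Length of Study lists enrollment before note collection. This is not a written blinding rule, but it agrees with the rest.

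**Step 2. What does 115 count?** The label is Number of Subjects. Under Population and the inclusion criterion, subjects are people implanted within the approved indications. On that usage an off-label or contraindicated case is not a subject, so 115 leans towards eligible cases. It is not labelled as such, and the wording could also describe all implanted cases.

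**Step 3. What if 115 is nevertheless the count before exclusions?** The plan gives no expected healing rate, exclusion share or precision target, so 115 has no derivation to reproduce. As an illustration, assume about 95% healed and use exact (Clopper-Pearson) 95% intervals. Cases are treated as independent, although 115 − 111 = 4 more cases than patients.

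| Assumed exclusions | n | Healed | Rate | 95% CI |
|---|---|---|---|---|
| none | 115 | 109 | 94.8% | 89.0–98.1 |
| 12 (about 10%) | 103 | 98 | 95.1% | 89.0–98.4 |
| 23 (20%) | 92 | 87 | 94.6% | 87.8–98.2 |

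The lower limit falls by 89.0 − 87.8 = 1.2 points in the least favorable row. The small differences in the rate come from rounding to whole cases.

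**Step 4. Where would a larger shift come from?** Removing one *non-healed* case from n, with x healed, changes the rate by x/(n − 1) − x/n = x/[n(n − 1)]. With x = 112 and n = 115 this is 112/(115 × 114) = 112/13,110 = 0.85 points: 112/115 = 97.4% (92.6–99.5) becomes 112/114 = 98.2% (93.8–99.8). The interval for 112/115 is 6.89 points wide, so one case is worth 0.854/6.89 = 0.12 of that width. The shift arises only because the removed case was chosen for its outcome. Step 1 shows that the plan does not support that kind of exclusion.

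**The case for a change.** The best case for the concern is that its literal statements are true. Three exclusions have no date, the healing item is open-ended, and no stage is attached to the 115. The plan does not say in words that eligibility is fixed before outcomes are seen. If someone did take the post-operative reading, the effect could grow beyond one case. With an assumed 109/115 = 94.8% healed, dropping three non-healed cases gives 109/112 = 97.3% (92.4–99.4), and dropping all six gives 109/109 = 100% (96.7–100). A sentence or two would close that door, at almost no cost.

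The literal statements stand. So does the point that the count is unlabelled, and because consent is part of enrollment, 115 could mean eligible or consented cases. The inference to bias does not stand. The worst case needs a reading that conflicts with the Population and Objectives entries, and nothing in the document suggests that outcomes will be used to judge eligibility. Whether the device's instructions for use close the open-ended list cannot be known from this document. A flow of cases identified, excluded and consented is good reporting practice, but its absence from a short synopsis does not make any rule or figure in it wrong.

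**Conclusion.** The concern does not hold. Read together, the entries place the exclusions before or at surgery. Followed that way, the plan yields a sound descriptive healing percentage for on-label cases. The unlabelled count then bears only on precision: about 1 point on the lower confidence limit, under an assumed healing rate near 95% and an assumed 20% excluded. The shift of about 0.85 points per case, and the worst case of 100%, apply only if non-healed cases are removed because of their outcome. All healing and exclusion counts used here are assumptions. The plan sets no comparator, target or margin, so no pass/fail conclusion depends on this point. What is left is a preference for more explicit wording.

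### Consent falls after surgery and before chart collection, with no stated route for eligible patients not enrolled, so the rates of this consecutive series may rest on a subset selected after the outcome

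*Combined protocol and SAP*

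**What the plan says.** All references are to the synopsis table of the Clinical Investigation Plan (CIP).

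- **Study Design:** "Single-center, Retrospective, Consecutive series".
- **Population:** "Consecutive series of subjects implanted with one of the DVR Plating System according to the approved/cleared indications". No first or last surgery date, screening log or other rule fixes which cases make up the series.
- **Inclusion/Exclusion Criteria:** the only inclusion criterion is implantation of a DVR plate within the approved indications. Consent is not listed as a criterion.
- **Length of Study:** three groups of activities, in this order: "Ethics Committee approval, patients' identification, consent and enrollment into the study"; then "Collection of baseline information available in medical notes from the pre-OP condition to the immediate post-OP and last consultation visit"; then "Conduct follow-up phone calls, data collection, analysis, and final report". The step at issue is "consent and enrollment into the study", in the first group.
- **Number of Subjects:** "115 cases (in 111 patients) implanted with the DVR Plating System". The entry does not say whether this is the number identified, enrolled or analysed.
- **Objectives:** "The primary objective is the assessment of performance by analyzing fracture healing". Safety, through the incidence of complications and adverse events, is secondary.
- **Statistical Analysis:** healing, revision and complication results are to be given as frequencies and percentages, and categorical data in general with 95% confidence limits. No denominator or analysis set is named.

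**The concern.** In a prospective study, refusal happens before the outcome exists. Here the operation, and everything recorded up to the last consultation, comes before the patient is asked. A patient who refuses, has died, has moved or does not answer is lost at a point where the loss can depend on how the wrist did. If the listed steps are followed literally, such a patient's chart is never abstracted, even though it may already hold the healing and complication data.

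What is at stake is the denominator of the primary healing rate and of the safety rates. The value of a consecutive series is that every eligible case counts. A rate among those who agreed and could be found is a different quantity, and a flow diagram would disclose the loss without changing the rate.

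**Working it through.** **Plan's own figure.** There is nothing to reproduce. 115 cases in 111 patients is a bare count, and the CIP gives no expected healing rate, precision target or expected enrolment share. Every share and rate below is therefore an assumption chosen to show scale. Consent is given per patient while rates are per case. With only 115 − 111 = 4 extra cases, I work at case level.

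**Step 1: what 115 could be.**

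- *Identified series, incomplete enrolment.* The identified series is consecutive, but fewer than 115 cases are analysed. At 70%, 80% and 90% enrolment, 115 × 0.7 ≈ 80, 115 × 0.8 = 92 and 115 × 0.9 ≈ 104.
- *Enrolled count, incomplete enrolment.* More cases must have been identified, and some were passed over. Rounding up, 115/0.9 gives 128, 115/0.8 gives 144 and 115/0.7 gives 165.
- *Complete enrolment, or chart use waived.* No subset arises and there is no problem.

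**Step 2: bounds if 115 is the identified count.** Assume 80% enrolment, so 92 are enrolled and 115 − 92 = 23 are not, and 89 of the 92 healed.

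- Observed: 89/92 = 96.7%, exact (Clopper-Pearson) 95% CI 90.8% to 99.3%.
- Worst case (none of the 23 healed): 89/115 = 77.4%.
- Best case (all 23 healed): (89 + 23)/115 = 112/115 = 97.4%.

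The worst case lies well below the lower confidence limit. Sampling-based limits do not cover this source of uncertainty.

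**Step 3: a milder scenario.** Assume 97% healing in the 92 enrolled and a rate q in the 23 not enrolled. The full-series rate is (0.97 × 92 + q × 23)/115.

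- q = 0.80: (89.24 + 18.4)/115 = 93.6%, a difference of 3.4 points.
- q = 0.90: (89.24 + 20.7)/115 = 95.6%, a difference of 1.4 points.

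If q = 0.97 there is no difference, and if q is higher the enrolled-only rate understates healing.

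**Step 4: complications, same 80% assumption.** With 5 of 92 enrolled cases having a complication:

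- Observed: 5/92 = 5.4%.
- Lower bound: 5/115 = 4.3%.
- Upper bound: (5 + 23)/115 = 28/115 = 24.3%.

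**Step 5: bounds if 115 is the enrolled count.** Assume 80% enrolment (144 identified, 29 not enrolled) and 109 of 115 healed.

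- Observed: 109/115 = 94.8%, exact 95% CI 89.0% to 98.1%.
- Bounds: 109/144 = 75.7% and (109 + 29)/144 = 95.8%.

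The reading of 115 changes the arithmetic but not the conclusion: at 80% enrolment the width is about 20 points either way (97.4 − 77.4 and 95.8 − 75.7).

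**The case against.** The best defence is that the consent wording comes from a list of activities, not from an eligibility rule or an analysis set. The only inclusion criterion is on-label implantation, and the Statistical Analysis entry does not confine rates to consenters. Consent pages are not part of the public text, so a waiver or a route for unreachable patients may be described there. This stands: the documents do not show that a self-selected subset will be analysed, only that nothing visible prevents it.

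A reader might be tempted by four stronger claims that the documents do not support.

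- *That one stated property must fail whichever way 115 is read.* It need not. If 115 is the identified series, that series remains consecutive, and nothing promises that all 115 will be analysed. With full enrolment there is no conflict at all.
- *That the rates will flatter the device.* Patients with poor results may be harder to reach. Equally, those with complications may return to the treating centre and be easier to find. The documents support neither direction.
- *That every outcome precedes consent.* Phone follow-up is planned after enrolment, so some data are new.
- *That PRWE is collected by phone.* The score is listed without a mode of collection.

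It is also fair to say that the milder rates in Step 3 (93.6% and 95.6%) lie inside the exact interval of 90.8% to 99.3%, and that a descriptive study with no threshold or test has no stated decision to overturn. That limits the weight of the point. It does not remove it, because selection error does not shrink as cases are added, and the reported percentages are the study's result.

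**Conclusion.** The concern holds in conditional form. The stated steps put consent between identification and chart collection, and the visible text provides no route for eligible patients not enrolled and no denominator. Unless consent is complete or chart use is waived, the healing, revision and complication rates will describe a subset formed after the charted outcomes. That does not establish that the series is not consecutive or that its rates are biased.

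The possible size runs from nothing, at full enrolment, to bounds about 20 points wide at an assumed 80%. Moderate assumptions at the same enrolment give 1.4 to 3.4 points. The likely size and the direction cannot be read from the documents. This is a cheap improvement that is worth making.

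**What to change.** 1. State the first and last surgery dates that define the series, and say whether 115 cases is the identified or the enrolled count.
2. Make all consecutive eligible on-label cases between those dates the denominator for chart-based endpoints (healing, revision, complications). Ask the ethics committee to agree to de-identified chart data for patients not enrolled.
3. Limit endpoints that need patient contact to patients reached, and state that denominator separately. Say how PRWE is collected so that it can be assigned to the right group.
4. Where chart use is not permitted, report the number not enrolled by reason. Give best-case and worst-case healing and complication rates over the full consecutive denominator as a sensitivity row beside the main estimate.

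**Cost.** CIP wording, one request within an ethics submission that is already planned, and two extra table rows. If enrolment proves complete, the sensitivity rows coincide with the main estimate and nothing is lost. The downside is that, with incomplete enrolment, the sensitivity figures will be wider and less favourable than the enrolled-only rates.

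### Are the fracture healing, osteotomy, revision and complication rates left without confidence limits, and does it matter that no interval method is named?

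*Combined protocol and SAP*

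**What the plan says.** The statistical plan is a single short paragraph in the synopsis table, under Statistical Analysis. It opens with "Data collected in the study will be summarized descriptively". Continuous variables then get "means, medians, standard deviation, minimum, maximum and 95% confidence intervals (CIs"). For categorical variables the rule is "Categorical data (e.g. gender) will be summarized using counts, percentages and 95% confidence limits". The sentence directly after it reads "Summaries of fracture healing and osteotomy rates, implant related revision rates and complication data will be presented as frequencies and percentages". No method of constructing an interval is given for either type of variable.

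Under Objectives, the primary aim is stated as "The primary objective is the assessment of performance by analyzing fracture healing". The safety aim includes "recording and analyzing the incidence and frequency of complications and adverse events", together with the relation of events to implant, instrumentation or procedure. Number of Subjects gives "115 cases (in 111 patients) implanted with the DVR Plating System". The plan contains no hypothesis test, comparator, performance goal, expected rate or precision target.

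**The concern.** Two adjacent sentences appear to set different rules. The general one attaches limits to categorical data and uses gender as its example. The specific one covers the outcomes that the study exists to estimate, and it names two of the three elements while leaving out the third. A specific sentence placed after a general one can be read as replacing it for the items listed. On that reading a baseline characteristic gets an interval and the primary endpoint does not.

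That would matter in a single-arm descriptive study, where the estimate and its precision carry most of the inferential content. A bare statement of no revisions, or of all fractures healed, in 115 cases looks stronger than the data allow.

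Two further gaps sit beside this one. The interval method is open, and methods can differ for proportions close to 0% or 100%. The safety objective also mentions both incidence and frequency, whereas the analysis sentence refers only to complication data. A binomial interval suits the proportion of cases with at least one complication. It does not suit a total of events that can recur within a case.

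**Working it through.** **Inputs.** The denominator is 115 cases in 111 patients (Number of Subjects), and the confidence level is 95% (Statistical Analysis). The plan gives no expected rates, so the healed counts below are assumptions that span a range. The plan states no interval or precision figure that could be reproduced.

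**Step 1: does the general rule reach these outcomes?** Each named rate is a proportion from a two-category variable. The reference to gender is introduced as an example, so it does not confine the rule to baseline items. The following sentence says which summaries will be shown and contains no word excluding limits. The two sentences can both be obeyed at once by giving the count, the percentage and the 95% limits. The text is therefore ambiguous but not contradictory.

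**Step 2: what would be lost if limits were left out?** With 0 events in n, the exact two-sided 95% upper limit is 1 - 0.025^(1/n). For n = 115 this is 1 - 0.025^(1/115) = 3.2%, and the matching lower limit for 115/115 healed is 96.8%. These follow from the count and the denominator alone, so a report that gives both lets any reader recover the interval.

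**Step 3: how much does the method matter?** Clopper-Pearson (exact) limits come from beta quantiles, with lower limit Beta(0.025; x, n-x+1) and upper limit Beta(0.975; x+1, n-x). Wilson limits invert the score test. Wald limits are p ± 1.96√(p(1-p)/n). At n = 115:

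| Healed (assumed) | % | Exact | Wilson | Wald |
|---|---|---|---|---|
| 115 | 100 | 96.8-100 | 96.8-100 | 100-100 |
| 113 | 98.3 | 93.9-99.8 | 93.9-99.5 | 95.9-100.7 |
| 109 | 94.8 | 89.0-98.1 | 89.1-97.6 | 90.7-98.8 |
| 103 | 89.6 | 82.5-94.5 | 82.6-93.9 | 84.0-95.2 |

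For 113/115, Wald is 0.9826 ± 1.96√(0.9826 × 0.0174/115) = 0.9826 ± 0.0239, which passes 100%.

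Exact and Wilson limits never differ by more than about 0.6 percentage points in this table. Wald lower limits are higher than exact ones by 1.5 to 3.2 points.

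The true coverage of nominal 95% limits is the sum of Binomial(115, p) probabilities over outcomes whose interval contains p. At true rates of 95%, 97% and 99% it is 92.6%, 86.0% and 68.4% for Wald, and 96.8%, 97.7% and 99.4% for Clopper-Pearson. For Wilson it is 95.1% at a true rate of 95% and 97.1% at 99%.

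**Step 4: does the choice of cases or patients matter?** The zero-event upper limit moves from 3.2% (n = 115) to 1 - 0.025^(1/111) = 3.3% (n = 111). Suppose four patients contribute two cases each and 107 contribute one, with complete within-patient correlation. The design effect is then (107 × 1 + 4 × 4)/115 = 123/115 = 1.07, and the standard error rises by √1.07 - 1 = 3.4% at most.

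**The case for a change.** The strongest argument for a change is that it would be nearly free and would remove a real ambiguity. The outcome sentence does leave limits out, directly after a sentence that includes them, and a literal reader could take the omission as deliberate. Even on the generous reading the method stays open, and settling it beforehand prevents a choice made after the results are seen. The Wald column shows that one familiar method performs poorly if healing is close to complete.

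The ambiguity and the missing method name both stand as observations. The step from there to a needed change does not. The Wald failures require two things that the plan does not state: that an analyst picks Wald, and that the rates lie near 100%. An analyst who meets an impossible upper limit or a zero-width interval has an obvious reason to use exact or Wilson limits, and these nearly coincide. A choice made after seeing the data would gain little, because there is no margin or performance goal to cross.

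On incidence versus frequency, the Objectives already name both ideas, and nothing in the plan promises a binomial interval for repeated events. Counting cases with at least one event, and listing total events separately, is ordinary reporting practice.

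**Conclusion.** No change follows. Read together, the two sentences give the healing, osteotomy, revision and complication rates 95% limits. The later sentence is loosely worded but does not exclude them. The unnamed method is a detail that a competent analyst will settle sensibly. At n = 115 the exact and Wilson limits agree to within about 0.6 percentage points for assumed healing between 89.6% and 100%, and the denominator question moves the zero-event limit by only 0.1 point. No stated figure is wrong, and no error rate, sample size or decision depends on the point.

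This rests on two assumptions: that the report gives counts with denominators, as the plan's reference to counts and frequencies implies, and that the analyst applies the general categorical rule to outcomes as well as to baseline data. If the analyst left the limits out, the report would be less informative, but the intervals for the case-level proportions could still be computed from the published counts.
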